4.3 Eligibility Criteria

We will seek to enroll up to 310 participants (up to 50 run-in participants, and 260 general participants), with the aim of a balance between male and female participants. Potential participants will be classified as outlined below using self-reporting of smoking habits.

4.3.1 Criteria for All Participants

All participants must meet all inclusion criteria:

- 18-65 years of age
- English speaking
- Smokes daily
- Smokes 5 or more cigarettes per day
- Owns and uses a smartphone (iPhone 5 and above, operating system iOS 9.0 and above, or, Android 4.4 and above, operating system Android 4.4 and above)
- Employed at least 20 hours per week
- Lives in the USA
- Understands and willing to sign the Informed Consent Form

While pregnant women are not specifically sought in this study, pregnancy is not an exclusion criterion, and pregnant women would be eligible should they meet the inclusion criteria and wish to participate. Pregnant women would be considered eligible for the following reasons: the risk profile of the device, the fact that recording smoking in the study is by self-report and the CONFIDENTIAL

modest participant stipend is not linked to smoking in any way, and potential participants reach out to the study team if they are interested in participating (i.e. recruitment is passive and wholly at the initiation of potential participants, who the study team have no visibility to unless contacted by the potential participant). While participants are deemed eligible to enter the study based on their self-report of smoking at least 5 cigarettes a day, they are not required or asked to smoke any particular amount (or at all) over the course study. Participants are asked to provide breath samples in the CO Breath Sensor device throughout the day, as they are able.

The general study (n=260) will employ non-proportional quota sampling as follows to ensure the study population mirrors the expected initial intended user population:

Age	18-29 year olds	30-60 year olds	61-65 year olds
	< 20 % of sample	Remainder	< 10 % of sample
Cigarettes Per Day (CPD)	5-10 CPD	11-30 CPD	> 30 CPD
	< 25 % of sample	Remainder	< 10 % of sample
Stages of Change*	Quit 30 days	Quit 6 months	Not interested
	≥ 20% of sample	≥ 20% of sample	≤ 20 % of sample
Sex	Male 40-60%	Female 40-60%	

^{*}Stages of Change question and answer choices: Are you seriously thinking of quitting smoking? A. Yes, within the next 30 days B. Yes, within the next 6 months C. No, not thinking of quitting

4.4 Subject Recruitment and Screening

Potential subjects will be identified via advertisement at outdoor locations (i.e. flea markets, outside of movie theaters, shopping malls, train stations, stores that sell cigarettes), print media (i.e., local newspapers, billboards), web media (i.e., Craigslist, Facebook, Survey Monkey, Instagram, Twitter, Google Ads, Reddit, smokefree.gov) and through clinical research recruiters ■. Respondents will be asked to provide contact information (phone) number, email address), and answer questions on smartphone ownership, employment status and hours worked per week, and smoking behavior using the Online Screening Form or through the clinical research recruiter, if applicable. Study staff will review each potential participant's responses to the eligibility questions. Potential participants who meet eligibility criteria (or those for whom it is unclear if they meet eligibility criteria due to an incomplete Online Screening Form) and meet non-proportional sampling needs will be contacted by phone, informed of the study and screened further if necessary (for example, collecting complete screening information, or clarifying duplicate entries). During this interaction, study personnel will inform the potential subject of the study details and will answer any questions. Potential participants will then determine if they would like to proceed with the study. Potential participants who would like to proceed will be emailed the online registration portal link, which includes the electronic informed consent

All subjects will have ample time to read the informed consent and ask questions of the study investigator team before signing informed consent.

4.5 Subject Stipend

Subjects will be offered a stipend for the study. Payment structure will be described during the screening phone call and in the Informed Consent Form. Participant compensation is tied to completion of study questionnaires and returning the CO Breath Sensor at the end of the study. Participants will be emailed payment after completion of each study questionnaire. Payment will be in the form of a Visa e-card. Subjects who are not compliant with the protocol despite efforts by study personnel may be terminated from the study. Subjects who are not able to complete the study for any reason will be compensated for their completed participation.

4.6 IRB Oversight

This study will be conducted with IRB oversight.

4.7 Study Environment Description

The entire study, including participant data collection of breath samples, logging cigarettes, completing daily activities and interacting with the coach, will be conducted in an ambulatory environment, with participants living their daily lives however is typical for them (work, home, school, etc.).

4.8 Study Personnel

The study team members will be trained by reading the study protocol, informed consent form, and reviewing the participant-facing content (BSA app, Pivot app). The study team members will have full training on the operation of the study devices and protecting human research participants.

4.9 Study Site

Study staff and management is headquartered at the Carrot office:

The entire study is conducted remotely; there are no study site visits for study participants.

4.10 Sample Size and Justification

Up to 50 participants will comprise the run-in group. The purpose of the run-in group is to provide baseline observations on the functioning of the BSA and Pivot app, and provide the opportunity to address unforeseen bugs or issues that arise prior to proceeding with the general study.

The target enrollment of 260 for the general study is estimated to yield 100 or more subjects completing the study at the last time point (3 months after the end of Secure). Based on power calculations, this will detect a 50% reduction in cigarettes, a mean change of 1 or greater in ratings assessing attitudes towards smoking, and will provide adequate confidence intervals to make historical comparisons.

5 Study Procedure and Schedule

5.1 Screening and Day 0

Study personnel will verify eligibility by reviewing the potential participant's responses to the Online Screening Form ; eligible participants (applies to both the run-in and general study participants) who meet non-proportional quota sampling needs (applies to general study participants) will then be called by study staff. During this call, any additional needed screening information is obtained, eligibility is confirmed, the study is described and the potential participant has the chance to ask questions. If the potential participant would like to proceed, the online registration form is emailed to the potential participant. Potential participants will be provided an access code at this time to allow access to the website.

Verification of identity and informed consent is performed during the screening phone call and during the online registration process. At this time, potential participants create a user login and password. An email is then generated and sent to the email address provided by the potential participant. To confirm identity, the potential participant must access their email and confirm through the provided link. The potential participant then reviews the electronic informed consent form on their own timeline and is provided study staff contact information should they have any questions. If the potential participant would like to proceed, they electronically sign the informed consent form

5.3 Pivot Journey

After set-up and onboarding, participants start the Pivot program. The Pivot program consists of four primary components:

- Periodic breath sampling using the CO Breath Sensor
- Cigarette logging
- Daily activities and challenges
- Coaching using in-app chat

During the study, participants submit periodic breath samples (suggested frequency is phase-dependent) while awake. Participants are instructed to log each cigarette they smoke using the Pivot app.

Participants are also asked to complete the activities presented in the Pivot app. Pivot app activities are educational in nature and intended to facilitate exploration and understanding of one's smoking behavior and attitudes. In addition, Build (the second phase of the program) includes challenges associated with activities; these challenges enable participants to develop skills to assist with quitting

In addition, participants will engage with a coach. The coach will initiate interactions with the participant by in-app chat throughout each phase of the study. The coach's primary role is to partner with the participant to explore how smoking impacts their time and financial resources, what purpose smoking serves in their life, their reasons for why they might want to quit, their interest and readiness in quitting, and provide support and encouragement during the quit process.

The Pivot program consists of 5 phases that are intended to be completed sequentially, with continuous engagement (i.e. no breaks in between). Acknowledging that challenging life events and circumstances occur, participants will be permitted to resume the Pivot program where they left off after up to two weeks of non-engagement/absence.

		-		
Δ	summary of each	i Pivot nhaca ic i	nravidad halawi	i
$\overline{}$	Summary of Cach	i i ivot pilase is i	provided below	
	,			

Explore			
Duration, pace, key components	 9 days, time based, one activity unlocks each 24 hours 		
Intent	 "Open the Door" "Turn on the light bulb" Raise awareness and build motivation 		
Activity/content	One activity is unlocked per 24h		
Cigarette logging	All cigs		
Suggested breath CO sampling protocol	 Hourly samples (10) a day for 9 days 		
Coaching frequency	4 coach-initiated touch-points in 9 days		
Study management	 If participant does not use the app at least once during the 2 days after onboarding (no cig logging, or CO sampling, or start/complete activity, or respond to coach outreach), study staff will call participant on days 3, 4 and 6 		

Build		
Duration, pace, key components	 1 day to 4 weeks based on recommended daily pace. Can be longer if content is not consumed daily. Daily activity+challenge available 	
Intent	 For those ready to quit, make a quit plan For those not yet ready to quit, raise readiness and confidence, then make a quit plan 	
Activity/Content	 28 activities and 28 associated challenges in 4 modules (7 activities and 7 challenges per): Prep to Quit (PTQ) Smoking & Health Motivation Matters Potential Pitfalls User starts on a specific module based on their responses to final Activity (9) of Explore. Users whose responses indicate they are ready to quit (score of 8 or higher on each of 3 questions about readiness, confidence and perceived difficulty of quitting), go straight to PTQ. Otherwise another module is prioritized. User must choose a quit date to unlock PTQ User can spend 1 day to 4 weeks in Build, or longer if they do the activities slower than daily 	
Cigarette logging	All cigs	
Suggested breath CO sampling protocol	Hourly samples throughout Build	
Coaching frequency	 3 to 4 touch-points per week If a user has not completed activities and/or hasn't had a coaching interaction within 3 days, the coach will reach out to the user to check in. 	
Study management	If participant does not use the app at least once in 7 days (no cig logging, or CO sampling, or start/complete activity, or start/complete challenge, or complete daily check-in, or respond to coach outreach), study staff will email on day 9, text on day 10, call on day 11, and call on day 13	

Mobilize				
Duration, pace, key components	7 days based on recommended daily pace			
Intent	Prepare for Quit Day			
Activity/content	 7 activities, daily pace recommended No time lock, but must finish all activities to move on User can finish faster or slower. Quit date must be set within 14 days, but user can push out quit date during Mobilize, and thus extend this phase of the program User prompted to change quit date if not all activities are completed User prompted to set earlier quit date if they finish all activities. 			
Cigarette logging	All cigs			
Suggested breath CO sampling protocol	 2 days of "intensive" sampling (hourly) to benchmark – beginning and end of Mobilize Remaining days in between are 3 breaths a day: morning, mid-day, evening 			
Coaching frequency	 Intro touch point to Mobilize with two interactions on completion of specific activities that prepare users for quit day. Wrap-up touch point to review quit plan If a user has not completed activities, milestones and/or has not had a coaching interaction within the past 2 days, the coach will reach out to the user to check in. 			
Study management	If participant does not use the app at least once in 7 days (no cig logging, or CO sampling, or start/complete activity, or start/complete challenge, or complete daily check-in, or respond to coach outreach), study staff will email on day 9, text on day 10, call on day 11, and call on day 13			

Quit				
Duration, pace, key components	 7 days from quit date, time based, activities are unlocked daily Daily check-in introduced Red 'guy' on Pivot app dashboard turns green, Crush-a-Craving button added 			
Intent	 Getting through the toughest week Lapse and relapse handling 			
Activity/content	 Daily check-in, must be completed to access rest of app One activity is unlocked per 24h 			
Cigarette logging	Daily check-in asks if user smoked previous day, if so, then directs them to log cig			
Suggested breath CO sampling protocol	 Encourage light use to see progress 3 breaths a day, morning, mid-day, evening Plus every time user has a craving 			
Coaching frequency	 Intro touch point to Quit with two strategic interactions after completion of smoke-free milestones (Quit: 24 hours and 72 hours) Wrap-up touch point to review progress, celebrate smoke-free milestones and identify areas of the quit plan that may need to be adjusted going forward – guide to move to Secure. If a user has not completed activities, milestones and/or has not had a coaching interaction within the past 2 days, the coach will reach out to the user to check in. 			
Study management	If participant does not use the app at least once in 7 days (no cig logging, or CO sampling, or start/complete activity, or start/complete challenge, or complete daily check-in, or respond to coach outreach), study staff will email on day 9, text on day 10, call on day 11, and call on day 13			

	Secure
Duration, pace, key components	11 weeks from quit dateDaily check-in
Intent	Lapse and relapse handling
Activity/content	Daily check-in with journaling
Cigarette logging	Daily check-in asks if user smoked previous day, if so, then directs them to log cig.
Suggested breath CO sampling protocol	No explicit sensor use schedule, but sensor is incorporated as follows: • Encourage people who find the 3 times a day useful to keep doing that. • Allow users to set their own milestones, some can be sensor related. Pivot app also gives trophies for breath samples associated with abstinence to augment this. "Take a breath samples to celebrate your smoke-free success."
Coaching frequency	 3-4 coach-initiated interactions per week for the first 3 weeks For users who achieve 30day PP at 3 weeks or 7 weeks in Secure, coaching frequency drops to once weekly, until/unless user indicates lapse or relapse.
Study management	 For the first 3 weeks: If participant does not use the app at least once in 7 days (no cig logging, or CO sampling, or start/complete activity, or start/complete challenge, or complete daily check-in, or respond to coach outreach), study staff will email on day 9, text on day 10, call on day 12, and call on day 14 For the remaining 7 weeks: If participant does not use the app at least once in 14 days (no cig logging, or CO sampling, or start/complete activity, or start/complete challenge, or complete daily check-in, or respond to coach outreach), study staff will email on day 16, text on day 17, call on day 19, and call on day 21

The following table details the different questions being asked of participants at specific time points over the course of the study.

		1	1	1	T	I	I	1	1	T
	Baseline	Explore	Build	Mobilize	Quit (1wk)	Secure - 1wk (2wk post Quit)	Secure - 3wk (1mo post Quit)	Secure - 7wk (2mo post Quit)	Secure - End (3mo post Quit)	Follow -up (6mo)
Cigarettes per day	х	Х	Х	х	х	Х	Х	Х	х	х
Tobacco Forms Used	Х		Х		Х		х	Х	Х	Х
Readiness to Quit (1-10)	х	Х	Х	Х						
Success, if were to quit (1-10)	х	х	Х	Х						
Difficulty staying quit, (1-10)	Х	Х	Х	Х						
Quitting Goal	х	Х	Х	х						
Nicotine Dependence		Х		Х						
7day Point Prevalence					х	х	х	Х	Х	х
30day Point Prevalence							х	Х	Х	х
Date of Last Cig					Х	Х	Х	Х	х	Х
Longest Smoke- free Interval					Х	X	X	Х	Х	Х
Quit Attempts					Х	Х	Х	Х	х	Х
NPS		Х	Х	Х	Х				х	
Coach NPS		X	Х	Х	Х				Х	
Quality of Life	Х								Х	Х
Cessation Medications	х			Х	х	×	×	Х		Х

Participants will receive an email, text or phone call from study staff to inform them they have a questionnaire to complete (

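### The 30-day point-prevalence item is first asked at a time point that falls nominally 28 days after the quit date, two days short of its own look-back window

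*Combined protocol and SAP*

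**What the plan says.** Section 4.2 lists 7-day and 30-day point-prevalence quit rates among the additional endpoints, in both the ITT and Per Protocol cohorts, without naming time points for either. The primary endpoint is phase completion.

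The calendar comes from section 5.3. The Quit table gives that phase as "7 days from quit date, time based, activities are unlocked daily". The questionnaire table then places the first Secure column at "Secure - 1wk (2wk post Quit" and the next at "Secure - 3wk (1mo post Quit". The 7-day row has six marks, beginning at the end of Quit. The 30-day row has four, beginning at three weeks in Secure. The row "Date of Last Cig" is marked at the end of Quit and at every later time point.

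One operational use of the 30-day item is stated. The coaching row of the Secure table lowers contact frequency "For users who achieve 30day PP at 3 weeks or 7 weeks in Secure".

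On timing, section 5.3 says "Participants will receive an email, text or phone call from study staff to inform them they have a questionnaire to complete"; the sentence breaks off there in the readable text. The same section lets participants resume the program "after up to two weeks of non-engagement/absence".

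**The concern.** Thirty-day point prevalence asks about the 30 days before the answer. If the question is first put 28 days after the quit date, the look-back reaches into days when a participant following the program was still expected to be smoking and logging cigarettes. For someone who stops exactly on the quit date, an on-time negative answer is literally correct, but it says nothing about whether the quit attempt has held.

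Two things are at stake. First, section 4.2 attaches no time points to the 30-day rate, so a rate at three weeks in Secure could be reported. It would then classify two people with identical quits differently because one opened the questionnaire a couple of days later. Second, the coaching row treats 30-day prevalence at three weeks in Secure as something a participant can achieve. On the nominal calendar, a participant who stopped on the quit date cannot achieve it.

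**Working it through.** **Inputs.** Explore 9 days, Build 1 to 28 days, Mobilize 7 days and Quit 7 days from the quit date (section 5.3); Secure 11 weeks = 77 days (section 4.2 and the Schedule of Study Activities); primary phase 14.5 to 18.5 weeks (Protocol Summary).

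**Step 1: reproduce the stated program length.** If Secure follows the 7-day Quit phase:

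- shortest: 9 + 1 + 7 + 7 + 77 = 101 days; 101 / 7 = 14.4 weeks
- longest: 9 + 28 + 7 + 7 + 77 = 128 days; 128 / 7 = 18.3 weeks

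Rounded to half weeks, this is the stated 14.5 to 18.5. Secure therefore starts at day 7 after the quit date and runs for 11 weeks.

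**Step 2: check the column labels.** Week w in Secure falls on day 7 + 7w after the quit date. For w = 1 this is day 14, which agrees with the label "Secure - 1wk (2wk post Quit".

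**Step 3: compare each time point with the 30-day window.**

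| Time point | Day after quit date | Margin over 30 days |
|---|---|---|
| Secure, 3 weeks | 7 + 21 = 28 | 28 − 30 = −2 |
| Secure, 7 weeks | 7 + 49 = 56 | 56 − 30 = +26 |
| Secure, end (11 weeks) | 7 + 77 = 84 | 84 − 30 = +54 |

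If both end days are counted, the shortfall at three weeks is one day. The first whole Secure week to reach 30 days is week 4, on day 7 + 28 = 35.

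**Step 4: compare with the 7-day item.** It is first asked at the end of Quit, day 7, when its window has just been reached. Only the 30-day item is first asked before its window can be filled from the quit date. The one-month column label hides the difference between 28 and 30 days.

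**Step 5: who is affected.** Someone who stops on the quit date and answers on day 28 has at most 28 days since quitting and is a non-abstainer on this item. The same person answering on day 30 can be an abstainer. Someone who stopped at least two days before the quit date can truthfully qualify on day 28.

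**The case against.** The strongest reply is that no specified analysis is harmed. The Protocol Summary and section 6.2 place the comparisons at entry, at the end of each phase and at exit, and Per Protocol membership in section 4.2 turns on the end-of-phase or exit survey. Three weeks into Secure is none of these. This stands, and it keeps the point minor. It does not remove it, because the item is collected, the endpoint is listed without time points, and the coaching row uses this very reading.

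A second reply is that point prevalence is not anchored to the quit date, so nothing is mismeasured, and that sustained quit is already an endpoint. Also fair: the negative answer is correct. The difficulty lies in reading a rate at this time point as a measure of success since quitting.

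A third reply is that a gap of one or two days is smaller than the uncertainty about when people answer. The notice sentence is cut off, so a timing rule may exist that cannot be seen. Participants may pause, may take longer to finish Quit, or may stop before the quit date. All of this stands, so day 28 must be called nominal and no size can be put on the effect.

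Two stronger readings are tempting. A reader might infer a nine-day gap, because the Secure table counts its 11 weeks from the quit date, and three weeks on that clock is day 21. The documents do not support this. The phases are meant to run in sequence, the first Secure column is labelled two weeks after quitting, and starting Secure at the quit date gives 9 + (1 to 28) + 7 + 77 = 94 to 121 days, or 13.4 to 17.3 weeks, which misses the stated length. The management row's first three weeks followed by "For the remaining 7 weeks" total 10 weeks. They fit a Secure phase that starts on day 7 and ends on day 77, which still puts the three-week point on day 28.

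A reader might also infer that a three-week 30-day rate would be close to zero. That would need nearly everyone to stop on the quit date and answer on the nominal day, and nothing in the documents says so.

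**Conclusion.** The point holds in a limited form and is minor. On the nominal calendar, the 30-day item is first asked two days too early (one day if both end days are counted) for a participant who smokes up to the quit date. A 30-day rate reported at three weeks in Secure would therefore depend partly on how promptly people answer. The direction, for on-time responders who stop on the quit date, is to understate abstinence since quitting; the size cannot be estimated from the documents.

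This rests on Secure starting at day 7, which the Quit duration, the column labels and the stated program length all support, and on an answer given on the nominal day.

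The scope is one mid-phase time point of an additional endpoint, plus the coaching row. On the nominal schedule the primary endpoint, 7-day prevalence and the 30-day readings from seven weeks in Secure onward are unaffected.

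**What to change.** Choose one of two, and state in section 4.2 the time points at which 30-day prevalence is reported.

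1. Send the three-week Secure questionnaire at least 30 full days after the quit date. The cost is a shift of a few days: the questionnaire no longer falls exactly at three weeks in Secure, and the coaching criterion is read at a shifted time.
2. Keep the timing. At three weeks in Secure, report a measure labelled as 28-day or since-quit-date abstinence, derived from "Date of Last Cig", which is already asked there, and report 30-day prevalence from seven weeks in Secure onward. The cost is one derived variable and no 30-day rate at one month.

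Under either option the coaching row must be reconciled with the resulting day count; no coaching rule is proposed here.

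As a separate minor matter, the Secure table's count of 11 weeks from the quit date and the 3 + 7 = 10 week split in its management row conflict with section 4.2, which requires 11 weeks spent in Secure. These should be reconciled. The stated program length supports 11 weeks after the Quit phase.

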
feedback on the experience is sought upon completion of the Secure phase of the Pivot App, or upon the end of the participant's engagement with the app, whichever occurs first. Upon return of the study device and completion of the questionnaire conducted 3 months after completing the primary phase of the

study, the study is considered complete.

Endpoint and analysis

We will compare the following variables at entry, after completion of each Pivot App phase, and/or at exit.

Engagement:

- Weeks of active engagement
- Phase completion
- Number of app opens

Smoking Behavior:

- Number of cigarettes smoked per day
- Quit attempts
- Quit rates: 7-day, 30-day point prevalence
- Sustained quit (continuous days quit)
- Smoking reduction (in participants who do not quit)

Responses to questionnaires:

- Measurements assessing attitude toward smoking
 - Readiness to quit
 - o Goals related to smoking behavior
 - Confidence to quit
 - o Difficulty maintaining quit
- Net Promoter Score (NPS)
- NPS, Coaching
- Nicotine Dependence
- Quality of Life

Schedule of Study Activities

	Screening	Day 0	Day 1	Pivot App - Explore (9 days)	Pivot App - Build (1 - 28 days)	Pivot App - Mobilize (7 days)	Pivot App - Quit (7 days)	Pivot App - Secure (11 weeks)	Exit - 3 mos after Secure or 3 mos after the end of participant's engagement with the app
Eligibility Confirmed	Х								
Informed Consent		Х							
Baseline Questions (demographics, thoughts about smoking)		Х	Х	х					
Receive COBSS*			Х						
Cigarette Logging**				Х	Х	Х	Х	Х	
Breath Sampling***				Х	Х	X	Х	Х	
Coach-Initiated Interactions				Х	Х	X	Х	Х	
Questionnaire			Х	Х	X	х	Х	Х	Х
Questionnaire (thoughts about smoking and the experience of using the device)								Х	
Exit questionnaire									Х
Return Breath Sensor									X
Study Completion									Х

^{*} COBSS received by participant only after confirmation of eligibility and provision of informed consent

^{**} Cigarette logging should stop at the beginning of the Quit phase of the Pivot App (assuming participant quits smoking), however, participants are asked to log all cigarettes, including those that occur during a lapse or relapse

^{***} Suggested breath sampling schedule varies from one phase to the next

Table of Contents

1		In	roduction 9		
	1.1		Background		9
	1.2		Study Rationale		10
	1.3		Potential Risks a	and Benefits	10
	1	.3.	1 Known Pot	tential Risks	10
	1	.3.	2 Known Pot	tential Benefits	10
	1	.3.	Risk Benef	fit Assessment	10
2		St	udy Objective		11

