1.2 Study Rationale

We will assess engagement, motivation, smoking behavior changes, nicotine dependence, smoking cessation rates, quality of life, retention and general feedback in smokers using the Pivot mobile smoking cessation program over a period of 3 months, with 3-month follow-up after program completion.

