6.2 Data Analysis

Data from the run-in participants will be analyzed separately from the data from the general study participants. Both cohorts will be analyzed using the ITT and Per Protocol definitions, and endpoints described previously.

Changes in measurements from baseline, to the end of each phase, to exit will be assessed. Participants will serve as their own controls and comparisons will be made to no change. One sample t-test will be used for numerical data. Fisher's Exact or Chi square will be used for categorical data.

All deviations from the study protocol will be identified, recorded and analyzed.

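### Nicotine dependence is scheduled only at the end of Explore and the end of Mobilize, so its change from baseline to exit under section 6.2 cannot be computed

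*Combined protocol and SAP*

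**What the plan says.** Nicotine dependence appears among the questionnaire endpoints in the Protocol Summary and in section 4.2, in both places as a bare entry with no instrument and no time point. Section 1.2 (Study Rationale) includes it in a list with a stated window: "We will assess engagement, motivation, smoking behavior changes, nicotine dependence, smoking cessation rates, quality of life, retention and general feedback in smokers" using the programme, "over a period of 3 months, with 3-month follow-up after program completion".

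Section 6.2 (Data Analysis) gives one general rule for all measurements: "Changes in measurements from baseline, to the end of each phase, to exit will be assessed". It adds: "Participants will serve as their own controls and comparisons will be made to no change". The Protocol Summary is looser: "We will compare the following variables at entry, after completion of each Pivot App phase, and/or at exit".

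The questionnaire table at the end of section 5.3, introduced as setting out which questions are asked when, has ten columns: Baseline, Explore, Build, Mobilize, Quit (1wk), four Secure points, and Follow-up (6mo). The row "Nicotine Dependence" is marked under Explore and Mobilize and nowhere else.

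**The concern.** A within-participant change needs a value before exposure and a value at the time of interest. For dependence the plan has neither the first nor, for any time after the quit date, the second.

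The earliest value is taken at the end of a phase whose stated intent is "Raise awareness and build motivation", after daily CO sampling and coaching. If that phase shifts reported dependence, the shift is already inside the starting value. The documents do not show that it does, but the data as scheduled could not tell. The later value falls in the phase that prepares for quit day, so nothing is recorded on dependence in people who later relapse, cut down or carry on smoking. A baseline that was not asked cannot be recovered once participants have started.

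**Working it through.** No sample size or power figure is at issue. The check sets the schedule against the analysis rule and then places the two measurements in time.

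**Reading the table.** The dependence row has ten cells, in column order: Baseline blank, Explore marked, Build blank, Mobilize marked, then six blanks from Quit (1wk) to Follow-up (6mo). Neighbouring rows read sensibly in the same grid, so a column shift is unlikely:

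- Cigarettes per day: all ten points.
- Readiness to quit: Baseline, Explore, Build, Mobilize.
- 7-day point prevalence: Quit (1wk) to Follow-up, six points.
- Quality of life: Baseline, Secure - End, Follow-up.

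**Contrasts available for dependence.**

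- Baseline to any of the nine later columns: 0 of 9, because Baseline is blank.
- Values at or after the quit date: 0 of 6.
- Pairs with both values scheduled: 1 (Explore and Mobilize).

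**Timing at the recommended pace.** Phase lengths from the section 5.3 phase tables and the Schedule of Study Activities: Explore 9 days, Build 1 to 28, Mobilize 7, Quit 7, Secure 11 weeks = 77 days.

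- Check against the plan's own figure: 9 + 1 + 7 + 7 + 77 = 101 days = 14.4 weeks, and 9 + 28 + 7 + 7 + 77 = 128 days = 18.3 weeks. The Protocol Summary states 14.5 to 18.5 weeks, so the phase lengths are read correctly.
- End of Explore: day 9.
- End of Mobilize: 9 + 1 + 7 = day 17, to 9 + 28 + 7 = day 44.
- Interval between the two values: 17 − 9 = 8 days, to 44 − 9 = 35 days.
- End of Secure: day 101 to 128. Follow-up, taking 3 months as 91 days: 101 + 91 = day 192, to 128 + 91 = day 219. Neither has a dependence value.

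**Exposure before the first value.** Suggested breath samples: 10 a day × 9 days = 90. Coach-initiated contacts: 4. These are suggested or planned amounts, not observed use.

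**Other sources of a baseline.** The Protocol Summary describes the baseline questionnaires as demographics, smoking history and attitude. Section 5.2 describes demographics and smoking behaviour. Neither names dependence. Cigarettes per day is asked at Baseline, but with no instrument named it cannot be assumed that a dependence score could be derived from it.

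**The case against.** The strongest reply is that section 6.2 is a general sentence that cannot apply to every row. Net Promoter Score and point prevalence have no Baseline mark either, the four attitude rows (readiness, success, difficulty, goal) also stop at Mobilize, and the Protocol Summary's and/or wording allows timing to differ by item. On that view, ending dependence at Mobilize is a design choice. This partly stands: the missing post-quit values could be intended. It does not explain the missing Baseline. The attitude rows have one. A satisfaction score has no meaning before use, and point-prevalence abstinence at entry is settled by the daily-smoking criterion. Dependence has a meaningful entry value that is simply unknown. If the post-quit gap is intended, sections 1.2 and 6.2 still need to say so.

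A second reply is that blank cells here are weak evidence. The Rev. B entry in section 9 says cessation-medication questions were added at Secure 11 weeks, yet that row is blank at Secure - End, and the questionnaires themselves are not in the public text. The schedule in the Protocol Summary also marks baseline questions under Explore, which blurs the two. This lowers confidence slightly. It does not show that a dependence baseline exists: the schedule row is described as demographics and thoughts about smoking, the section 5.3 table keeps Baseline and Explore as separate columns, and section 6.2 defines no substitute baseline.

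A reader might also infer more than the documents support:

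- *That a stated study objective fails.* The objectives in the Protocol Summary and section 2 do not name dependence. It appears in the rationale and as an additional endpoint.
- *That no value follows any attempt to quit.* The app includes practice quits (section 3.2), and section 4.2 counts any 24 hours without smoking as an attempt, so attempts can precede the end of Mobilize. Only the formal quit date marks the limit.
- *That 8 to 35 days bounds the interval.* Section 5.3 lets Build run longer and Mobilize run faster or slower.

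**Conclusion.** The point holds as a mismatch between what is scheduled and what is to be analysed. As the plan stands, no dependence change from baseline can be computed to any phase or to exit. The single computable contrast is Explore to Mobilize, roughly 8 to 35 days at nominal pace, in participants who reach the end of Mobilize and who had 9 days of the programme before the first value. The endpoint is therefore not wholly unmeasured, but what is measured is a short pre-quit change in a retained subset.

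This rests on the section 5.3 table being a complete record of what is asked. The consequence is confined to one additional endpoint. Phase completion, quit rates, cigarettes per day and the sample-size reasoning in section 4.10 do not depend on it. It should be corrected because the correction is cheap and a missed baseline is permanent.

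**What to change.** In the section 5.3 questionnaire table, add nicotine dependence at Baseline, before device set-up, and at Secure - End and Follow-up for participants still smoking. Keep the Explore and Mobilize values as interim points. Name the instrument.

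In section 6.2, state the dependence analysis explicitly: change from Baseline to Explore and to Mobilize, and change from Baseline to Secure - End and to Follow-up among those still smoking. Report the last two as results in a selected subgroup. Give no overall mean at those times unless the named instrument can be scored in people who have stopped. Section 4.10 expects 100 or more participants at the last time point, so the subgroup at Follow-up is that number less those abstinent.

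If post-quit items are not wanted, still add the Baseline mark, and restrict sections 1.2 and 6.2 to pre-quit change in dependence.

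The cost is a few items in up to three questionnaires that are already sent, and short wording changes. The downside is slightly longer surveys.
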